Research Protocol

Project Name: Characteristics of Subgingival Microbiota in Patients with Stage III-IV Periodontitis in Response to Nd:YAG Laser-Assisted Therapy

August 16, 2024

1. Research Background and Rationale

Periodontitis is a microbially associated, host-mediated chronic inflammatory disease. Stage III-IV periodontitis, representing the advanced phase of disease progression, is characterized by severe alveolar bone loss and irreversible clinical attachment loss (CAL). According to the latest Global Burden of Disease Study, periodontitis ranks as the sixth most prevalent condition globally, with Stage III-IV cases constituting a significant proportion of affected individuals^[1].

The primary therapeutic objectives in periodontitis management are plaque control and inflammation resolution. Conventional scaling and root planing (SRP), while foundational, exhibits inherent limitations including incomplete biofilm removal and iatrogenic tissue trauma^[2]. The neodymium-doped yttrium-aluminium-garnet (Nd:YAG) laser (wavelength: 1064 nm), a near-infrared laser modality, demonstrates selective absorption for melanin and hemoglobin while maintaining low water absorption coefficients (0.61 cm^{-1}). This unique photophysical property enables deep tissue penetration and localized photothermal effects^[3]. Recognized for its potent bactericidal, hemostatic, and soft tissue ablation capabilities, Nd:YAG laser has emerged as a minimally invasive adjunct to periodontal therapy. Nevertheless, the response patterns of subgingival microbiomes to Nd:YAG laser-assisted treatment remain insufficiently characterized in the current literature.

2. Study Objectives

This study aims to comparatively evaluate the clinical efficacy of Nd:YAG laser-assisted scaling and root planing (SRP) versus conventional SRP alone in the treatment of stage III-IV periodontitis. Furthermore, we seek to investigate the effects of Nd:YAG laser adjunctive therapy on the compositional structure and diversity of subgingival microbiota. By elucidating the potential

role of Nd:YAG laser in modulating subgingival microbial equilibrium, this research will provide novel theoretical insights and evidence-based guidance for the clinical management of periodontitis.

3. Study Design

3.1 Study Setting and Participants

From August 2024 to March 2025, 120 patients with stage III-IV periodontitis were recruited from the Department of Stomatology, The First Affiliated Hospital of Sun Yat-sen University, according to predefined eligibility criteria. All participants provided written informed consent. The study subjects were randomly allocated to either the conventional subgingival scaling and root planing (SRP) group (n=62) or the Nd:YAG laser-assisted SRP group (n=63).

3.1.1 Inclusion Criteria (1) Diagnosis of stage III-IV periodontitis based on the 2018 classification system jointly proposed by the European Federation of Periodontology (EFP) and the American Academy of Periodontology (AAP)^[4, 5], with: Maximum interdental clinical attachment loss (CAL) ≥ 5 mm, and Radiographic bone loss extending to the mid-third of the root or beyond; (2) Age 18–80 years; (3) Minimum of 14 natural teeth remaining in the dentition; (4) Willingness to provide informed consent and comply with study protocols.

3.1.2 Exclusion Criteria (1) Systemic conditions affecting periodontal treatment outcomes; (2) Periodontal therapy within the past 6 months; (3) Recent use of antibiotics or medications associated with gingival enlargement; (4) Pregnancy or lactation; (5) Acute periodontal lesions; (6) Inability to cooperate.

3.2 Sample Size Calculation

Based on preliminary data, the mean difference in post-treatment probing depth (PD) between the SRP group and Nd:YAG-assisted SRP group was estimated at 0.45 mm, with a standard deviation (SD) of 0.58 mm. Using PASS 25.0 software, we calculated the required sample size with the following parameters: Significance level (α): 0.05 (two-tailed) and Power (1- β): 90%. The initial computation indicated a minimum of 18 participants per group. To account for a potential $\leq 20\%$ dropout rate, the final sample size was adjusted to at least 23 subjects per group (46 total).

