3.4 Data Management and Statistical Analysis Plan

Data collection and entry were performed according to standardized operating procedures (SOPs), with researchers manually entering all study data into a unified Excel spreadsheet.

Statistical analyses were conducted using SPSS 25.0 software. For continuous variables, the Shapiro-Wilk test was employed to assess normality of distribution. Normally distributed measurement data were expressed as mean \pm standard deviation (SD), with between-group comparisons analyzed using independent samples t-tests and within-group pre-post treatment comparisons evaluated with paired t-tests. Categorical data were presented as percentages (%) and compared using chi-square tests. A two-sided P-value < 0.05 was considered statistically significant for all analyses.

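### The 18 per group in Section 3.2 does not follow from its own inputs: a two-group t-test needs 36 per group, and 18 gives about 62% power, not 90%

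*Protocol*

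**What the plan says.** Protocol Section 3.2 takes its inputs from preliminary data. The difference in post-treatment probing depth "was estimated at 0.45 mm, with a standard deviation (SD) of 0.58 mm". Alpha is 0.05 two-sided, power is 90%, and the calculation was run in PASS. The result is given as "The initial computation indicated a minimum of 18 participants per group". After an allowance for up to 20% dropout, "the final sample size was adjusted to at least 23 subjects per group (46 total" in all.

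Three other places fix the design that this calculation has to serve:

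- Section 3.1 describes patients randomised to two parallel groups, and reports 120 recruited with arms of 62 and 63.
- Section 3.3.1 reduces each parameter to one mean per patient.
- Section 3.4 has "between-group comparisons analyzed using independent samples t-tests".

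**The concern.** A difference of 0.45 mm against an SD of 0.58 mm is a standardised effect of about 0.78. Eighteen per group is too few to detect an effect of that size with 90% power in a two-sided, two-sample comparison. The gap is a factor of two, so rounding or a choice between normal and t formulas cannot explain it.

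This is the protocol's only sample-size justification. If it is wrong, the 90% power claim is false at the stated minimum. A trial run to that minimum (46 enrolled, about 36 completing) would miss its own target difference nearly four times in ten, where the text implies one in ten. The figure could also be carried into the trial report or reused to plan a later study.

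**Working it through.** **Inputs (all from Section 3.2 unless noted).** Difference 0.45 mm; SD 0.58 mm, taken as the common within-group SD between patients; two-sided alpha 0.05; power 90%; equal groups (23 per group, 46 total); independent-samples t-test (Section 3.4); one value per patient (Section 3.3.1).

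**Step 1. Standardised effect.** d = 0.45 / 0.58 = 0.776.

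**Step 2. Trying to reproduce 18.** Alternative settings for a two-group test do not give it:

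| Setting | n per group, normal | n per group, t |
|---|---|---|
| Two-sided, 90% (as stated) | 35 | 36 |
| One-sided, 90% | 29 | 30 |
| Two-sided, 80% | 27 | 28 |
| One-sided, 80% | 21 | 22 |

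The one-sample (or paired) normal formula does give it: n = (1.960 + 1.282)² / d² = 10.507 / 0.602 = 17.46, rounded up to 18. This leaves out the factor of 2 that a two-group comparison needs. The paired t-test itself would need 19.48, so 20. Alternatively, 36 / 2 = 18, as if a per-group 36 had been read as a total and split. Both are guesses at the origin; neither fits two independent groups.

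**Step 3. The correct two-group calculation.**

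- Normal approximation: n = 2 × (1.960 + 1.282)² / d² = 2 × 10.507 / 0.602 = 34.91, so 35 per group.
- Noncentral t: 35.90, so 36 per group.

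**Step 4. Dropout.** The protocol's step is right in itself: 18 / 0.8 = 22.5, rounded up to 23. Applied to the corrected number: 36 / 0.8 = 45 per group, 90 total.

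**Step 5. Power for 0.45 mm with SD 0.58 mm (two-sided t-test).**

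| Completers per group | Power |
|---|---|
| 18 | 61.9% |
| 23 | 73.0% |
| 36 | 90.1% |
| 49 / 50 (62/63 less 20%) | 96.9% |
| 60 / 60 (120 recruited) | 98.8% |
| 62 / 63 | 99.0% |

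**Step 6. What would make 18 right.** For 90% power at 18 per group, the t-test needs d = 1.112. That means a difference of 1.112 × 0.58 = 0.65 mm at the stated SD, or an SD of 0.45 / 1.112 = 0.40 mm at the stated difference. Neither value appears in the protocol.

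**The case against.** The arithmetic is not in dispute; the counter-case concerns weight and remedy.

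**Consequence.** Section 3.1 reports recruitment of 120, or 125 by summing the arms. Either count exceeds the corrected 90. Even 48 per group (120 less 20%) leaves 96.4% power. The 23 per group is also worded as a floor and not as a stopping target, so the loss of power at 18 per group is hypothetical for this trial. That stands: the comparison as recruited is not underpowered on these inputs. It does not make the stated sample size and power correct.

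**Which number is wrong.** Section 3.2 does not say what the 0.58 mm refers to. If it were the SD of a difference between two independent patients, the within-group SD would be 0.58 / √2 = 0.41 mm, and 18 per group would give 89.2% power by the t-test. So the SD could be misdescribed and the 18 nearly right. Nothing in the text supports this unusual reading, and it still falls short of 90% (19 per group by t). What stands is narrower: the protocol never defines its SD, so the sponsor has to confirm the definition. It should not be asserted on the sponsor's behalf.

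**Origin of the 18.** How the figure arose is conjecture. The finding does not depend on it.

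**Conclusion.** The sample size is wrong as written. On the stated inputs and the named test, 36 completers per group are needed, not 18. The minimum enrolment with 20% dropout is 90, not 46, so the stated figure is about half of what it should be. Power at 18 per group is about 62%.

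This rests on reading 0.58 mm as the within-group, between-patient SD of the per-patient mean, which is the natural reading for a parallel-group design analysed by an independent-samples t-test. The practical effect is confined to the justification, because reported recruitment exceeds the corrected minimum. The correction should still be made, since the claim can be shown false from the protocol's own numbers.

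**What to change.** In Section 3.2:

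1. Change the pre-dropout minimum from 18 to 36 per group, and the dropout-adjusted minimum from 23 per group (46 total) to 45 per group (90 total).
2. State what the SD of 0.58 mm measures. If the sponsor confirms that it is the between-patient SD of the per-patient mean, the figures above apply. If it is something else, give the within-group SD actually used, name the PASS procedure and recompute.
3. Add the power at the actual enrolment: about 99% at 62 and 63 with no loss, and about 97% after 20% loss. Section 3.1 gives both 120 and 62 + 63 = 125, so settle the count first. The conclusion is the same for either.

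The cost is wording and figures in one section. No additional patients and no change to design or analysis are required.

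### The planned size of 46 is not reconciled with the 120 recruited and arms of 62 and 63, and the stated 90% power fits neither number

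*Protocol*

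**What the plan says.** Section 3.2 of the protocol bases the sample size on probing depth (PD). The difference in post-treatment PD "between the SRP group and Nd:YAG-assisted SRP group was estimated at 0.45 mm", "with a standard deviation (SD) of 0.58 mm". The error rates are "Significance level (α): 0.05 (two-tailed) and Power (1- β): 90" per cent. From these it derives 18 participants per group, allows for up to 20% dropout, and states that "the final sample size was adjusted to at least 23 subjects per group (46 total").

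Section 3.1 describes a larger trial: "From August 2024 to March 2025, 120 patients with stage III-IV periodontitis were recruited", allocated to the "conventional subgingival scaling and root planing (SRP) group (n=62) or the Nd:YAG laser-assisted SRP group (n=63"). The two arms sum to 62 + 63 = 125, not 120.

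Section 3.4 names the test: "between-group comparisons analyzed using independent samples t-tests". The calculation in 3.2 should therefore be the one for two independent means.

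**The concern.** A reader takes three things from a sample size section: how many patients the trial needed, its power, and the difference it was built to detect. Here all three come from a number, 46, that is well below half of what section 3.1 reports. Dropout cannot account for the gap, because 46 already includes the 20% allowance. No sentence gives a target above 46 or a reason for exceeding it.

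What is at stake is interpretation. A trial with arms of 62 and 63 can reach significance on a PD difference clearly smaller than the 0.45 mm planned for, and section 3.2 does not say so. It also leaves the impression that 46 patients would have given 90% power, which its own inputs do not support.

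**Working it through.** **Inputs.** From 3.2: difference δ = 0.45 mm, SD σ = 0.58 mm, two-sided α = 0.05, power 90%, dropout up to 20%. From 3.4: independent-samples t-test. From 3.1: 120 recruited, arms of 62 and 63.

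**Step 1: the plan's own figures.** The dropout step reproduces: 18 / 0.8 = 22.5, rounded up to 23 per group, 46 in total. The 18 does not. For two independent means the normal approximation is

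n per group = 2(z₀.₉₇₅ + z₀.₉₀)² σ²/δ² = 2 × (1.960 + 1.282)² × 0.58²/0.45² = 2 × 10.51 × 1.661 = 34.9, rounded up to 35.

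The exact noncentral-t calculation gives 36. No other two-sample setting tried gives 18: one-sided 90% needs 29 to 30, and two-sided 80% needs 27 to 28. Without the factor of 2 (the one-sample or paired formula) the result is 10.51 × 1.661 = 17.5, rounded up to 18. Eighteen is also half of 36. Either could be the source, and the protocol does not say which.

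**Step 2: the requirement from the stated inputs.** 36 / 0.8 = 45 per group, 90 in total.

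**Step 3: power for 0.45 mm at each size.** The noncentrality is δ / (σ√(1/n₁ + 1/n₂)) with n₁ + n₂ − 2 degrees of freedom. At 62/63, for example, it is 0.45 / (0.58 × 0.1789) = 4.34; at 23/23 it is 0.45 / (0.58 × 0.2949) = 2.63.

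| Arms | Where the size comes from | Power for 0.45 mm |
|---|---|---|
| 18 / 18 | 3.2, evaluable | 61.9% |
| 23 / 23 | 3.2, no dropout | 73.0% |
| 36 / 36 | corrected requirement, evaluable | 90.1% |
| 48 / 48 | 120 less 20% | 96.4% |
| 50 / 50 | 62/63 less 20%, rounded | 97.0% |
| 60 / 60 | 120 split equally | 98.8% |
| 62 / 63 | 3.1, as allocated | 99.0% |

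Rounding the dropout down to 49/50 gives 96.9%.

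**Step 4: difference detectable with 90% power, SD 0.58 mm.** 62/63: 0.34 mm. 60/60: 0.35 mm. 50/50: 0.38 mm. 48/48: 0.39 mm. At 18/18 it is 0.65 mm, so the planned 0.45 mm does not match the size in 3.2 either.

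**Step 5: the gap.** Against the stated 46: 120/46 = 2.6 and 125/46 = 2.7. Against the corrected 90: 120/90 = 1.33 and 125/90 = 1.39. Most of the apparent excess therefore comes from the error in the 18, but an unexplained 30 to 35 patients remain after it is corrected.

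**The case against.** The strongest reply is that 3.2 sets a minimum. Enrolling more than a minimum satisfies it, and extra patients do not by themselves invalidate a t-test. That stands: 62 and 63 do not strictly contradict a floor of 23. It is also fair to say that the trial is better off with its actual size, since 46 would have been too few for 0.45 mm. What the reply does not supply is a reason for 120 or 125, or a correct statement of power at any size.

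A reader might infer something stronger: that recruitment had no end point, or that it was continued past 46 because of accruing results, so that the 5% error rate is compromised. The protocol does not support this. Section 3.1 gives a recruitment window and a count. They are reported in the past tense and are not declared as a target or rule, but they are not nothing. No section mentions an interim comparison or a data-driven extension. A statement on interim looks is commonly left to the SAP, which is not shown, so its absence here is no evidence that a look took place.

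A reader might also infer that 90% is right for 46 and that the trial simply over-enrolled. Step 3 shows otherwise: 46 gives 73% at best.

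**Conclusion.** The concern holds as a failure to reconcile sections 3.1 and 3.2, together with a power figure that fits neither. The stated 90% should read 73% at 23 per group (62% at 18 evaluable per group) and 99% at 62/63 (97% after 20% dropout). The requirement from the stated inputs is 36 evaluable per group, 90 in total after dropout, so both 120 and 125 exceed it by about a third or slightly more.

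The consequence is limited. Power for 0.45 mm is ample at the reported size, and neither the test nor its error rate is shown to be at fault. What is wrong is the stated basis of the trial: its size, its power and the difference it can detect.

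These figures assume that 0.58 mm is the common SD of post-treatment PD within each group, as the wording of 3.2 suggests, and that PD is compared once per patient by an unpaired two-sided t-test. The after-dropout figures assume the full 20% loss, equal in both arms.

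**What to change.** In section 3.2:

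1. Correct the calculation. With the present inputs it is 36 evaluable per group, and 36 / 0.8 = 45 per group, 90 in total. If 18 came from other inputs or another formula, state them and show that they match the unpaired comparison in 3.4.
2. State the one target number that governed recruitment, and the reason for it if it exceeds 90.
3. Replace the total of 46 and the 90% by the power and detectable difference at that number. For 62/63: 99% power for 0.45 mm, or 0.34 mm with 90% power; after 20% dropout, 97% and about 0.38 mm.

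In section 3.1, resolve 120 against 62 + 63 = 125 so that both sections carry the same number.

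The cost is wording in two sections. No patients are added, and neither the analysis nor the significance threshold changes.

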3.3 Study Procedures

3.3.1 Periodontal Examination

One week after supragingival scaling, a single-blinded periodontist performed full-mouth examinations at baseline and 3-month follow-up, following the WHO Oral Health Surveys Basic Methods guidelines^[6]. For each tooth, six sites (mesiobuccal, midbuccal, distobuccal, mesiolingual, midlingual, distolingual) were assessed for probing depth (PD), clinical attachment loss (CAL), gingival index (GI), plaque index (PI) and bleeding on probing (BOP). The mean value of each parameter per patient was recorded as the final measurement.

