3.3.3 Subgingival Plaque Sampling and Microbiome Analysis

Subgingival plaque sampling procedure: Subgingival plaque samples were collected from six designated teeth (#16, #21, #24, #36, #41, #44) at baseline and 3-month follow-up, with adjacent

teeth substituted if target teeth were missing. After isolation with sterile cotton rolls and removal of supragingival plaque, subgingival plaque was obtained using sterile Gracey curettes and immediately placed in 1.5 mL sterile microtubes containing phosphate-buffered saline (PBS). All samples were stored at -80°C until analysis. The collected samples were subsequently sent to MajorBio Corporation for 16S rDNA high-throughput sequencing (V3-V4 hypervariable regions, Illumina platform). Bioinformatic analysis was performed using QIIME2 pipeline with SILVA 138 database for taxonomic classification. The sequencing results were then integrated with clinical parameters for comprehensive cross-sectional and longitudinal analyses to evaluate microbial shifts following treatment.

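### Should the microbiome-clinical analyses use clinical means over the six plaque-sampled teeth instead of the full-mouth mean?

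*Protocol*

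**What the plan says.** Under section 3.3.1 of the protocol a masked periodontist "performed full-mouth examinations at baseline and 3-month follow-up". Probing depth, attachment loss, gingival index, plaque index and bleeding are read at several positions on each tooth ("For each tooth, six sites"). The readings are then condensed: "The mean value of each parameter per patient was recorded as the final measurement".

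Section 3.3.3 uses a narrower frame for the microbiology: "Subgingival plaque samples were collected from six designated teeth (#16, #21, #24, #36, #41, #44", at the same two visits, with neighbouring "teeth substituted if target teeth were missing". The material is "immediately placed in 1.5 mL sterile microtubes containing phosphate-buffered saline (PBS"; the section does not say whether the six samples are pooled, or how many sites per tooth are curetted. On the joint use of the two data sets it says: "The sequencing results were then integrated with clinical parameters for comprehensive cross-sectional and longitudinal analyses". The stated purpose is to assess how the microbiota shift after treatment.

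The inclusion criteria in section 3.1.1 set the smallest dentition: "Minimum of 14 natural teeth remaining in the dentition".

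**The concern.** The two data sets describe different parts of the mouth. The clinical value is an average over all teeth, and the microbial value comes from six. The full-mouth mean is the only clinical summary the protocol defines, so it is natural to suppose that it is what gets correlated with the sequencing results. Most of the sites behind it would then lie on teeth that gave no plaque.

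If the microbial profile depends on the local state of the sampled teeth, readings from the other teeth add noise and pull the associations towards zero. A mean over the sampled teeth would seem an easy improvement, because those teeth are already probed at both visits. The microbiome is in the project title and among the objectives, so the pairing is not a side issue.

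**Working it through.** The protocol gives no figure for this pairing, so there is nothing of its own to reproduce. The check asks how far the two summaries can differ, and which of them the difference favours.

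**Inputs from the protocol.** Six sampled teeth (3.3.3); six sites per tooth (3.3.1); at least 14 teeth (3.1.1).

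**Assumed inputs.** 28 teeth as the upper case; exchangeable teeth with unit variance and a within-patient tooth correlation *p* of 0.1 to 0.5; a true association of *r* = 0.40.

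**1. Share of sites on unsampled teeth.** The sampled teeth contribute 6 × 6 = 36 sites.
- 14 teeth: 14 × 6 = 84 sites; (84 − 36)/84 = 48/84 = 57%.
- 28 teeth: 28 × 6 = 168 sites; (168 − 36)/168 = 132/168 = 79%.

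**2. Agreement of the two summaries.** The variance of a mean over *k* teeth is *p* + (1 − *p*)/*k*. The six teeth are part of the *N*, so the covariance of the two means equals the variance of the full-mouth mean, and

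c = √{[*p* + (1 − *p*)/*N*] / [*p* + (1 − *p*)/6]}.

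Example, *p* = 0.1 and *N* = 28: √[(0.1 + 0.9/28)/(0.1 + 0.9/6)] = √(0.1321/0.25) = 0.727.

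| *p* | c, *N* = 14 | c, *N* = 28 |
|---|---|---|
| 0.1 | 0.811 | 0.727 |
| 0.3 | 0.917 | 0.883 |
| 0.5 | 0.958 | 0.942 |

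**3. Case A: plaque is tied to the mouth only through the sampled teeth.** An association of 0.40 with the six-tooth mean appears as 0.40 × c with the full-mouth mean: 0.324, 0.367, 0.383 (*N* = 14) and 0.291, 0.353, 0.377 (*N* = 28). Here the six-tooth mean is the better covariate.

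**4. Case B: plaque reflects the patient's overall level.** The correlation of a *k*-tooth mean with the patient-level component is √{*p* / [*p* + (1 − *p*)/*k*]}. Dividing the six-tooth value by the full-mouth value gives √{[*p* + (1 − *p*)/*N*] / [*p* + (1 − *p*)/6]}, which is c again. Now the six-tooth mean is the weaker covariate, by the same factor of 0.73 to 0.96.

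**5. Which case applies?** The protocol does not say. Read in two-digit tooth notation, the listed teeth are a molar, an incisor and a premolar in the upper jaw and the same three types in the lower jaw, with all four quadrants represented. They are fixed by position and not chosen by pocket depth or severity. Such a set can reasonably be read as standing for the whole mouth, which is case B.

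**6. Is the full-mouth pairing actually stated?** Section 3.3.1 fixes the patient's final clinical value. Section 3.3.3 refers only to clinical parameters and names no summary, level or model for the joint analysis. Nothing says that the site readings are discarded; section 3.4 has all study data entered into the spreadsheet. A full-mouth examination and index-tooth sampling can coexist without contradiction.

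**The case for a change.** The strongest argument for the concern is that the protocol itself, and not a missing SAP, fixes one final value per patient, fixes a different sampling frame for plaque, and commits to combining them. If only the means were kept, or substitute teeth were not recorded, no later SAP could restore a match. Substitution could also change the sampled teeth between visits.

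Part of this stands. The frames do differ, the site counts are right, and the full-mouth mean is the only summary defined. In case A with weakly correlated teeth (*p* = 0.1, 28 teeth) the loss reaches 27%, which is not trivial.

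The rest does not carry the point. Loss of the readings is a possibility that the text does not state. Whether samples are pooled, how many sites are curetted and which teeth were used at each visit are details the protocol leaves open, and being silent on them is not stating something wrongly. The same silence weakens the proposed alternative: without knowing the curetted sites, even a 36-site mean may not match the plaque, and it averages fewer sites than the 84 to 168 of the full mouth.

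**Conclusion.** The concern does not hold. The pairing of six-tooth plaque with a full-mouth mean is an inference from the text. How a clinical covariate is derived for an association analysis is commonly settled in the SAP, which may exist but is not available here.

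Preferring the six-tooth mean is a trade-off, not a correction. The wrong choice costs a factor of 0.73 to 0.96 in either direction, or 0.88 to 0.96 if *p* is 0.3 to 0.5. These sizes rest on the assumed tooth correlation, on 28 teeth as the upper case, and on exchangeability, which is doubtful for a fixed mix of incisors, premolars and molars. That the loss is the same in both directions does not depend on the value of *p* or *N*, though it does rest on the exchangeable model.

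The stated objectives are clinical efficacy by arm and the laser's effect on microbial composition and diversity, and neither depends on this pairing. Patients are randomised individually and treated over the full mouth, so a patient-level clinical value fits the design. Reporting both summaries would be a reasonable sensitivity analysis, but its absence from the protocol is not an error.

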3.3.2 Periodontal Treatment Protocol

Periodontal treatment was performed by a trained periodontist using a standardized quadrant approach, with half-mouth treatments completed per session separated by one-week intervals to ensure patient comfort and procedural consistency. Both treatment groups received full-mouth scaling and root planing using an EMS AIR-FLOW MASTER PIEZON® ultrasonic scaler and Gracey curettes, followed by comprehensive oral hygiene instructions and scheduling for 3-month follow-up visits.

The experimental group additionally received immediate Nd:YAG laser therapy post-SRP using a Wiser Waterlase MD system (Vista Dental) with manufacturer-recommended settings (150mJ/pulse, 20Hz frequency, water level 1 and air level 3 coolant). The laser was applied in a continuous zig-zag pattern across root surfaces and pocket linings, maintaining a 30° angle and delivering 2-second irradiation per treatment site to ensure thorough antimicrobial coverage while minimizing thermal damage to surrounding tissues.

All procedures were conducted under local anesthesia when clinically indicated, with strict adherence to infection control protocols and standardized patient positioning. Treatment fidelity was maintained through operator calibration, use of timer-controlled laser application, and periodic quality assurance checks to ensure consistent intervention delivery across all study participants throughout the trial duration.

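### The full-mouth mean is the only outcome summary, so a laser benefit confined to pockets would be diluted by a factor the protocol does not let one calculate

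*Protocol*

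**What the plan says.** Protocol 3.3.1 describes the examination: "a single-blinded periodontist performed full-mouth examinations at baseline and 3-month follow-up", with six sites probed per tooth and no depth threshold. It then fixes the outcome: "The mean value of each parameter per patient was recorded as the final measurement". It names no summary limited to pockets and no stratum by baseline depth.

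Three other places bear on this:

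- Section 3.1.1 sets eligibility by a worst-site criterion, "Maximum interdental clinical attachment loss (CAL) ≥ 5 mm", with radiographic bone loss, and asks for "Minimum of 14 natural teeth remaining in the dentition". It requires no minimum number or share of pockets.
- Section 3.3.2 describes the added treatment: "The laser was applied in a continuous zig-zag pattern across root surfaces and pocket linings". It gives a time per treatment site but does not define such a site by depth.
- Section 3.2 sizes the trial on a single contrast: "the mean difference in post-treatment probing depth (PD) between the SRP group and Nd:YAG-assisted SRP group was estimated at 0.45 mm". The SD paired with it is 0.58 mm. The section does not say whether these are full-mouth or pocket values.

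Section 3.4 compares groups with independent-samples t-tests and does not mention adjustment for baseline.

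**The concern.** With at least 14 teeth and six sites each, at least 14 × 6 = 84 readings become one number per patient. A patient can qualify on a few bad sites and contribute many shallow ones. A shallow site has little depth to lose, so if the laser works mainly in pockets, the mean averages sites that can respond with sites that hardly can. The mix also differs between patients for reasons unrelated to treatment.

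The stated aim is clinical efficacy in stage III-IV disease. With the full-mouth mean as the only summary, a null result could not separate no laser effect from an effect that was averaged away.

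**Working it through.** **Inputs from the Protocol.** Difference d = 0.45 mm, SD = 0.58 mm, two-sided α = 0.05, power 90%, 18 per group before dropout (3.2); 62 and 63 allocated (3.1; these sum to 125, while the same section says 120 were recruited); t-test (3.4).

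**Input not in the Protocol.** f, the share of averaged sites that are pockets. A range is used.

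**1. The plan's own figure.** For two independent groups, n = 2 × SD² × (1.960 + 1.282)² / d² = 2 × 0.3364 × 10.507 / 0.2025 = 34.9, so 35 per group (36 by the t-test). The stated 18 does not reproduce. Without the factor 2 (one-sample or paired formula) the result is 17.5, which rounds up to 18. This is a separate matter, and 62/63 exceeds 36.

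**2. Dilution.** If the effect in pockets is e and shallow sites gain nothing, the full-mouth difference is f × e and the dilution is 1/f.

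**3. If 0.45 mm were a pocket effect and 0.58 mm the SD of the full-mouth mean.** The standard error is 0.58 × √(1/62 + 1/63) = 0.104 mm. Power is about Φ(f × 0.45 / 0.104 − 1.96); the table gives the exact t-test values.

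| f | Dilution | Full-mouth difference (mm) | Power at 62/63 |
|---|---|---|---|
| 60% | 1.7 | 0.27 | 73% |
| 50% | 2 | 0.225 | 58% |
| 40% | 2.5 | 0.18 | 41% |
| 33% | 3 | 0.15 | 30% |
| 25% | 4 | 0.113 | 19% |
| 20% | 5 | 0.09 | 14% |

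A smaller full-mouth SD shrinks the loss. For f = 50% and 33%, power is 88% and 55% at SD 0.40 mm, and 99% and 79% at SD 0.30 mm.

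**4. If 0.45 mm and 0.58 mm are already full-mouth values.** Power at 62/63 is 99%. The detectable full-mouth difference is 0.104 × (1.960 + 0.842) = 0.29 mm at 80% power and 0.104 × (1.960 + 1.282) = 0.34 mm at 90%. For an effect confined to pockets:

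- The planned 0.45 mm needs a pocket effect of 0.45 / f: 0.9 mm at f = 50% and 1.35 mm at f = 33%.
- 80% power needs 0.29 / f: 0.58 mm at f = 50% and 0.87 mm at f = 33%. Smaller pocket benefits have less than 80% power.

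**5. How much is averaging and how much is lack of adjustment.** Two site-level simulations assumed a 0.30 mm effect in pockets only. Simulation A used 150 sites per patient, 62 patients per arm and 400 trials. Site variation was also assumed, so read these for direction only. Power at f of about 30% / 50%:

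| Analysis | Simulation A | Simulation B |
|---|---|---|
| Full-mouth mean, unadjusted | 33% / 59% | 44% / 70% |
| Pocket mean, unadjusted | 91% / 93% | 96% / 98% |
| Full-mouth mean, baseline-adjusted | 79% / 90% | 82% / 94% |
| Pocket mean, baseline-adjusted | 95% / 97% | 99% / 100% |

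Adjustment alone adds 46 / 31 points in A and 38 / 24 in B to the full-mouth analysis. Moving from the adjusted full-mouth mean to the adjusted pocket mean then adds 16 / 7 and 17 / 6. When the laser is assumed to act at shallow sites too, the adjusted full-mouth mean does better than the adjusted pocket mean.

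**The case against.** The full-mouth mean is a sound patient-level summary: it gives one value per patient and avoids treating sites as independent. It is also the only probing-depth outcome the protocol defines, so the natural reading is that 0.45 mm and 0.58 mm are on that scale. Power is then 99%. The low powers in step 3 come from calling 0.45 mm a pocket effect while keeping 0.58 mm as the full-mouth SD, a combination the documents do not state. Simulation A itself implies full-mouth SDs of about 0.33 to 0.38 mm. Section 3.3.2 sets no depth limit on the laser, so an effect confined to pockets is an assumption. Much of the simulated loss disappears with baseline adjustment. Analyses by baseline depth could also be left to an SAP that is not shown.

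Most of this stands, and it limits the size of the point. A reader might infer that the effect is diluted two- to three-fold as a matter of fact, or that power is only 30% to 58%. The documents support neither, because they give no pocket share, no effect by depth and no scale for 0.45 mm. A reader might also infer that site readings are thrown away. Section 3.3.1 does not say so, and section 3.4 has all study data entered in the spreadsheet.

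The appeal to an SAP does not remove the point. Section 3.3.1 itself names the mean as the final measurement, so this is a stated rule and not only a detail left open.

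**Conclusion.** The point holds in a conditional form. The protocol makes the full-mouth mean its only summary of each parameter. If the laser acts mainly in pockets, that summary dilutes the effect by 1/f, with f unknown: 2- to 3-fold for f of 50% to 33%, and 1.7- to 5-fold over 60% to 20%, assuming no gain at shallow sites.

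Whether planned power is affected depends on the unstated scale of 0.45 mm and 0.58 mm. On the full-mouth reading none is lost (99% at 62/63), but a pocket-confined benefit below about 0.58 to 0.87 mm (f of 50% to 33%, SD 0.58 mm) would have less than 80% power in the unadjusted t-test.

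The defect is that nothing stands beside the mean; the mean itself is valid. Since the advantage of a pocket summary reverses after adjustment if shallow sites also respond, it should supplement the full-mouth mean and not replace it.

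**What to change.** - **3.2:** state whether 0.45 mm and 0.58 mm refer to the full-mouth mean or to pocket sites.
- **3.3.1:** say that site-level readings are kept, and keep the full-mouth mean.
- **3.3.1 and 3.4:** prespecify, as a key supporting analysis, the between-group difference in patient mean PD (and CAL) over sites that were pockets at baseline. Use a prespecified cut-off, for example baseline PD of at least 4 mm, with sites fixed at baseline and one value per patient. The protocol contains no cut-off, so the sponsor must justify one.
- **3.4:** adjust both the full-mouth and the pocket mean for their own baseline value.

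The comparison should be between groups only. Sites selected for depth at baseline tend to read shallower on repeat probing even without treatment, so within-group change at those sites would be inflated. If outcomes have already been compared by group, label the pocket analysis as post hoc.

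The cost is a few lines of text, one more prespecified comparison and the cut-off to defend. The readings are already taken, so no visits or patients are added.
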